8.7.3 Re-initiation of Dose Escalation

If dose escalation is terminated due to the criteria noted above, reduced and/or repeat dose levels (as allowed per protocol) may be administered to provide additional data regarding the frequency and/or severity of AEs.

If the SRC agrees that these additional data suggest that the observations that initially resulted in a termination of dose escalation were not attributable to study medication, then dose escalation may be allowed to continue.

8.8 Study Termination or Withdrawal of Subject/Patient from Study

8.8.1 Study Termination

If the Sponsor terminates or suspends the study, the Investigator or his/her designee should promptly inform the IEC (and/or regulatory authorities where required) of a temporary halt including the reason for such an action (see also Section 12.1.10).

8.8.2 Subject/Patient Discontinuation or Withdrawal

Subjects/patients may withdraw from the study at any time without prejudice to their future medical care by the physician or at the institution. Furthermore, a subject/patient may also be discontinued at any time should they meet the criteria defined in Section 12.1.9.

The withdrawal of a subject/patient from the study should be discussed where possible with the Medical Monitor prior to withdrawal. If the subject is discontinued or withdraws from the study, the final evaluations are to be performed as completely as possible.

8.8.3 Subject's/Patient's Follow-up after Study Discontinuation or Withdrawal

The subjects/patients will be advised that participation in these investigations is voluntary. Furthermore, the subjects/patients may request that from the time point of withdrawal no more data will be recorded and that all biological samples collected during the study will be destroyed.

In the case of premature discontinuation or withdrawal, the safety assessments scheduled for the EOS examination will be performed as soon as possible after study drug administration, as per Investigator judgement, unless the subject/patient withdrew informed consent. A safety follow-up visit will be performed as per Investigator judgement, unless the subject/patient withdrew informed consent. PK and PD assessments after early discontinuation will be performed upon mutual agreement between the Investigator and the Sponsor.

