9.1.4 Reporting of Adverse Events

All AEs occurring from the (first) dose administration and up to Follow-Up must be recorded on specific AE pages of the eCRF (note: only AEs for randomized subjects/patients will be recorded in the eCRF) see also Section 8.3.2.1.

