9.1.5 Follow-up of Adverse Events

Adverse events must be followed until resolution, stabilization or up to EOS. Adverse events assessed as related must be followed until resolution, stabilization or to a maximum of 28 days after the EOS.

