12.1.9 Stopping rules for Subject/Patient

Should a subject/patient experience an AE or SAE that meets the following criteria, the subject/patient may be immediately discontinued from the study:

- Any AE or SAE in the judgement of the Investigator or subject/patient justifies withdrawal due to its severity, nature, or requirement for treatment, regardless of the causal relationship to the study drug.
- Clinically relevant test procedure results which endanger the subject/patient.

The reason(s) will have to be recorded on the appropriate page of the eCRF for each prematurely discontinued subject/patient.

For discontinued subjects/patients, the assessments scheduled for the EOS examination will be performed as soon as possible after study drug administration.

If the Sponsor terminates or suspends the study, the Investigator should promptly inform the IEC/IRB (and/or regulatory authorities where required) of a temporary halt including the reason for such an action.

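### Sections 8.8.3 and 12.1.9 disagree on PK and BSSL sampling at an early EOS examination, and no section asks a discontinued, consenting subject to keep later visits in Parts 2 and 3

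*Protocol*

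**What the plan says.** Four parts of the Protocol bear on a subject who stops early.

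- **8.8.3** provides that "the safety assessments scheduled for the EOS examination will be performed as soon as possible after study drug administration, as per Investigator judgement", unless consent was withdrawn. It adds "A safety follow-up visit will be performed as per Investigator judgement, unless the subject/patient withdrew informed consent", and "PK and PD assessments after early discontinuation will be performed upon mutual agreement between the Investigator and the Sponsor". ADA is not named.
- **12.1.9** says that a subject with a qualifying AE or SAE is one for whom "the subject/patient may be immediately discontinued from the study" applies. It then states: "For discontinued subjects/patients, the assessments scheduled for the EOS examination will be performed as soon as possible after study drug administration". It does not limit this to safety assessments and has no judgement clause or consent exception.
- **8.8.2** refers to 12.1.9 for the discontinuation criteria and says that "the final evaluations are to be performed as completely as possible".
- **Section 9** sets the event windows. Under 9.1.4, "All AEs occurring from the (first) dose administration and up to Follow-Up must be recorded on specific AE pages of the eCRF". Under 9.1.5, "Adverse events assessed as related must be followed until resolution, stabilization or to a maximum of 28 days after the EOS". Section 9.2.2.3 requires new SAEs to be reported until EOS. Section 9.2.3 makes reporting optional after EOS or after 28 days from drug discontinuation, whichever is earlier.

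Section 6.2.1 plans about 90 days of follow-up after treatment in Part 3. Section 6.3.4 gives a half-life of about 19 days. The SAP says nothing about visits after early discontinuation.

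**The concern.** Because 8.8.2 points to 12.1.9, both rules apply to the same person discontinued for an AE, and they call for different samples at the early examination.

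The larger matter is what follows. After an early EOS, the protocol provides one safety visit at the Investigator's discretion and PK/PD sampling if agreed. It does not ask a consenting subject who has been discontinued from the study to return for the remaining visits. In a first-in-human antibody study, the later exposure, ADA status and AEs of someone stopped for an AE are informative, and each active subject is 1 of 6 (16.7%) of a cohort's active arm.

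The analysis rules do not make up for missing data. SAP 7.2 imputes nothing. The Immunogenicity set (SAP 6.1.3) needs only one post-dose sample, so a Part 2 patient with the 4-hour and Day 8 samples enters it without any later ADA result.

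**Working it through.** **1. The two rules side by side**

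| | 8.8.3 | 12.1.9 |
|---|---|---|
| Early EOS content | Safety assessments | All assessments scheduled for EOS |
| Investigator judgement | Yes | Not mentioned |
| Consent exception | Yes | Not mentioned |
| PK and BSSL | By agreement only | Included, being scheduled at EOS |
| ADA | Not named; 8.11.2 lists immunogenicity under safety | Included |
| Later visits | One discretionary safety visit | None |

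The firm conflict is over PK and BSSL.

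**2. Planned sample counts reproduced**

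- Part 2 PK: Day 1 at four times, plus Days 2, 3 (optional), 4, 8, 14, 21, 35, 49, 63 and 90 = 14. Table 8-4 has 4.0 x 14.
- Part 2 BSSL: Day 1 twice, plus the same ten later days = 12. Table 8-4 has 4.0 x 12.
- Part 2 ADA: Day 1 twice, plus Days 8, 21, 49 and 90 = 6. Table 8-4 has 3.5 x 6.
- Part 3 PK: 20, and ADA (Days 1, 29, 57, 85, 113, 169): 6. Table 8-5 has 4.0 x 20 and 3.5 x 6.

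In the extracted text of Table 5-2, the PK and BSSL rows show no Day 90 mark. The Table 8-4 counts are reached only with Day 90, so it is taken as scheduled.

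**3. Drug still present**

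Sections 6.2.1 and 8.7.1 describe 28 days as Tmax and one half-life. With a half-life of about 19 days, implied Tmax = 28 − 19 = 9 days after dosing, about Day 10.

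- Log-linear decline after Tmax: C/Cmax at 28 days = 0.5^(19/19) = 0.50; at 84 days 0.5^(75/19) = 0.065; at 89 days 0.5^(80/19) = 0.054.
- One-compartment model with ke = ln2/19 = 0.0365 per day and ka = 0.251 per day (solved for Tmax of 9 days): 0.58, 0.076 and 0.063.

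Concentration is therefore about 50–58% of Cmax at 28 days, against about 5–8% at the planned EOS (89 days after the dose in Part 2, 84 days after dose 4 in Part 3).

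**4. Part 2 example: early EOS on Day 8, nothing later**

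- Day 8 is 7 days after dosing, before the implied Tmax.
- Not collected: 6 of 14 PK, 6 of 12 BSSL and 3 of 6 ADA samples.
- Share of AUC0-inf covered by 7 days, one-compartment: 1 − (ka·e^(−7ke) − ke·e^(−7ka))/(ka − ke) ≈ 0.12.
- Section 8.11.1.1 obtains the terminal rate constant by log-linear regression on the terminal phase. There are no such points, so T1/2, CL/F, Vz/F and AUC0-inf cannot be derived for this patient.
- If Follow-Up in 9.1.4 means the early EOS and no safety visit is held, recording of new AEs ends 90 − 8 = 82 days early.

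**5. Part 3 (MD1) example: discontinued after dose 2 on Day 29**

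- 12 of the 20 PK samples fall after Day 29. Six profile dose 4 (Day 85 at 4 h, Days 86, 88, 92, 95, 99) and three fall after Day 113 (Days 140, 154, 169). That leaves 12 − 6 − 3 = 3 relevant to this subject up to Day 113: Days 57, 85 and 113.
- ADA samples up to Day 113: 3 (Days 57, 85, 113).
- Section 8.1.2.2 ties the Part 3-only PK endpoints to the last dose, and 8.1.2.1 marks T1/2, CL/F and Vz/F for Parts 1 and 2. The main loss here is therefore late safety and ADA information.

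**The case against.** The strongest reply is that leaving PK and PD after discontinuation to agreement is a deliberate choice in a small, descriptive Phase I study, and that safeguards exist: final evaluations as complete as possible, a safety visit, AE recording up to Follow-Up, SAE reporting until EOS and follow-up of related AEs. Investigator and Sponsor may agree to collect everything. This stands as a limit: loss is possible, not certain. It does not remove the conflict over PK and BSSL, and none of these provisions sets a visit schedule after an early EOS.

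Several stronger readings are tempting, but the documents do not support them.

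- *The early ADA sample is also in dispute.* Section 8.11.2 lists immunogenicity among safety parameters, so 8.8.3 can be read as requiring it. Only later ADA samples are exposed.
- *New non-serious AEs go unrecorded.* Section 9.1.4 makes no exception for early stoppers and can be read as running to the scheduled Follow-Up. What is missing is a visit or contact at which to ask.
- *A Part 3 subject who only stops dosing is released from visits.* Nothing releases such a subject from Table 5-3. A clarifying sentence is enough.
- *A loss is likely.* Zero drop-outs among 40 in Part 1 gives a one-sided 95% upper limit of 1 − 0.05^(1/40) = 7.2%. That is a ceiling, not an estimate. It also covers consent withdrawals, whom the fix does not affect, and Parts 2 and 3 were already ongoing at this version.
- *Such a subject cannot be replaced.* The exception in 8.8.4 may qualify either replacement or the need for agreement, so no weight is put on it.

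**Conclusion.** The point holds in limited form. For a subject discontinued for an AE, 8.8.3 and 12.1.9 differ on PK and BSSL at the early examination. No section asks a consenting subject discontinued from the study to attend later scheduled visits.

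In Part 2, an exit at Day 8 without later sampling would leave one active patient of six without terminal-phase parameters. In Part 3 the main exposure is late safety and ADA data. It matters because concentration is still about half of Cmax at 28 days; that figure rests on the protocol's own description of 28 days and on log-linear decline. The 12% AUC share rests on a one-compartment model.

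Part 1 is unaffected, being complete with no drop-outs. The timing phrase that counts from study drug administration is a drafting slip and does not itself lose data. Overall this is a cheap improvement of modest importance.

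**What to change.** Use one rule in 8.8.3 and 12.1.9. Unless consent is withdrawn:

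- (a) The full EOS assessments, including PK, ADA and BSSL, are done promptly after the *discontinuation*, not timed from study drug administration.
- (b) In Part 2, subjects discontinued by the Investigator are asked to keep the remaining scheduled visits, with AE, PK and ADA assessments, to Day 90. A single Day 90 visit would not do: after a Day 8 exit it adds only one point beyond the implied Tmax, which cannot support a terminal slope.
- (c) In Part 3, subjects discontinued by the Investigator are asked to keep the scheduled AE, PK and ADA visits to at least about 84 days after the last dose. In MD1 these visits already exist: Day 85 (85 − 1 = 84), Day 113 (113 − 29 = 84), Day 140 (140 − 57 = 83) and Day 169 (169 − 85 = 84) for doses 1 to 4. Day 140 has no ADA sample, so a subject stopping after dose 3 needs either one 3.5 mL sample there or the Day 169 sample. MD2 follows its own schedule. State also that subjects who only stop dosing stay on the Table 5-3 safety visits to Day 169.
- (d) AE and SAE recording (9.1.4, 9.2.2.3, 9.2.3) runs to the last of these visits and never ends earlier than the current text requires.

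The cost is protocol wording and, for each early stopper, a few visits and samples that are nearly all planned already. No analysis set changes, Part 1 is not reopened, and subjects who withdraw consent are unaffected.

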8.8.4 Subject/Patient Replacement

Drop-outs might be replaced but only upon mutual agreement between the Investigator and the Sponsor, unless withdrawal is due to a drug-related AE. The replacing subject/patient will receive the same treatment as assigned to the subject/patient whom he/she replaces.

8.9 Treatment Exposure and Compliance

Records of study drug used, dosages administered, are kept during the study. Study drug accountability is performed on an ongoing basis by the study staff and checked by the CRA/monitor during site visits and at the completion of the study.

All drug administrations will be done under direct medical supervision.

8.10 Treatment Assignment and Blinding

8.10.1 Assignment of Subject/Patient Numbers

Subjects/Patients will receive a 4-digit number on Day 1 before study drug administration ([Table 8-6](#)). The assignment of number and code for subject/patient identification is based on the obligation for anonymity.

Table 8-6: Assignment of Study Codes to Subjects/Patients

Cohort	Subject/Patient numbers	Replacement numbers
Healthy subjects		
Cohort 1	0001 – 0008	1001 – 1008
Cohort 2	0009 – 0016	1009 – 1016
Cohort 3	0017 – 0024	1017 – 1024
Cohort 4	0025 – 0032	1025 – 1032
Cohort 5	0033 – 0040	1033 – 1040
Cohort 6 (optional)*	0041 – 0048	1041 – 1048
RA patients		
Cohort 7	0101 – 0108	1101 - 1108
Healthy subjects		
Cohort MD1	0201 - 0208	1201 - 1208
Cohort MD2	0301 - 0308	1301 - 1308

*Optional 6th cohort not run

Subjects/patients who replace discontinuing subjects/patients after randomization on Day 1 will receive the number of this subject/patient +1000, e.g., subject/patient 1006 will replace subject/patient 0006, subject/patient 2006 will replace subject/patient 1006, etc. The substitute subject/patient will receive the treatment assigned to the withdrawn subject/patient.

In the case of discontinuation of a subject/patient before randomization, the substitute subject/patient will receive the same number as the subject/patient he/she replaces.

8.10.2 Treatment Assignment

Subjects/patients will be randomized to any of the treatments assigned for that cohort. The randomization code is stored securely. It is accessible only to authorized persons who are not involved in the conduct and analysis of the study, until time of un-blinding. Individual sealed randomization codes are kept at the participating sites, and these are used for emergency un-blinding only.

Unused sealed code envelopes will be archived.

Randomization is controlled by the study drug packaging. The number on the subject/patient packaging equals the randomization number. Subjects/patients must be randomized in a consecutive order starting with the lowest subject number.

Randomization will be performed by the Biostatistics department of QPS Qualitix Taiwan, according to Qualitix Taiwan SOPs. The randomization code and the randomization list will be generated using SAS version 9.4 or the last available version at time of randomization.

The randomization code will be un-blinded and made available for data analysis only after study closure, i.e., when the study has been completed, the protocol deviations determined and the clinical database declared complete, accurate, and locked.

8.10.3 Double-blinding

The study is performed in a double-blind fashion. The Investigator and study staff (including processing lab personnel), the subjects/patients, the CRAs/monitors and the Sponsor's staff will remain blinded to the treatment until study closure. The investigational drug and its matching placebo are indistinguishable. The labels of the syringes will be double blind and the packaging of the placebo/active syringes identical. Only after preparation of the syringe is completed, it will be handed over by pharmacy staff to the staff of the clinic.

The randomization code will be kept strictly confidential. It is accessible only to the pharmacist on site, who is not involved in the conduct and analysis of the study, and will keep the randomization scheme strictly confidential.

The bioanalytical laboratory will only analyze the samples of subjects/patients receiving SOL-116, and not the samples of subjects/patients receiving placebo. Therefore, the bioanalytical laboratory will receive the randomization list from the biostatistician. The bioanalytical laboratory will not share this list with other parties and will blind all PK results before sending these to other team members.

8.10.4 Emergency Procedure for Unblinding

The Investigator receives emergency envelopes for each subject/patient containing the identity of the study drug dispensed. The Investigator and the study staff must remain blinded to the subject's/patient's treatment assignment, even if the subject/patient refuses to participate in any study procedures or experiences an AE. The identity of the study drug may be revealed only if the subject/patient experiences a medical emergency whose management would be improved by the knowledge of the blinded treatment assignment.

The occurrence of any code break during the study must be clearly justified and explained by the Investigator. Before opening the emergency envelope, every attempt must be made by the Investigator to discuss the intended code break with Lipum AB. In all cases, the Sponsor must be informed as soon as possible before or after the code break.

Any code break must be documented on the emergency envelope and in a detailed report with the date and time of the code break and signed by the Investigator. This report is to be attached to the source documents and the date and time of code break will be documented in the eCRF.

The CRA/monitor checks the emergency envelopes according to the Monitoring Plan (MP).

8.11 Study Parameters

8.11.1 Pharmacokinetic Parameters

The serum PK parameters for SOL-116 will be derived by non-compartmental analysis of the serum concentration-time profiles.

The following PK parameters have been defined:

- Area under the concentration-time curve from time zero to infinity (AUC_{0-inf});
- Maximum observed serum concentration (C_{max});

- Time to C_{\max} (T_{\max});
- AUC from time zero to time t of the last measured concentration above the limit of quantification (AUC_{0-t});
- Terminal elimination half-life ($T_{1/2}$);
- Apparent volume of distribution (V_z/F);
- Apparent total body clearance (CL/F).

In multiple dosing part, C_{trough} , time to steady state and accumulation ratio will also be assessed.

Attainment of steady-state conditions will be determined by visual inspection of the pre-dose serum concentrations.

8.11.1.1 Calculation of Pharmacokinetic Parameters and Assumptions

The measured individual serum concentrations of SOL-116 will be used to directly obtain C_{\max} and T_{\max} .

AUC_{0-t} will be calculated according to the linear up/log down trapezoidal method using the measured concentration-time values above the lower limit of quantification (LLOQ). $AUC_{0-\infty}$ will be calculated by combining AUC_{0-t} and AUC_{extra} . AUC_{extra} represents an extrapolated value obtained by C_t/λ , where C_t is the last serum concentration measured above the LLOQ and λ represents the terminal elimination rate constant determined by log-linear regression analysis of the measured serum concentrations of the terminal elimination phase. The half-life of SOL-116 will be calculated as follows: $T_{1/2} = \ln 2 / \lambda$.

The PK parameters will be based on actual blood sampling times [h] (relative to the corresponding administration time) rounded to two digits and negative pre-dose times will be set to zero.

Please refer to Section 10 for more information on statistical methodology.

8.11.2 Safety and Tolerability Parameters

Baseline is defined as the last value measured prior to SOL-116 administration (vital signs, ECG, laboratory parameters), unless otherwise specified.

The following parameters have been defined as parameters regarding safety and tolerability:

- Clinical laboratory evaluations;
- Injection site reactions;
- AEs;
- Immune reactions (e.g. hypersensitivity, cytokine release syndrome, immunogenicity);
- Vital signs;
- Physical examination;
- ECGs (3-lead telemetry and 12-lead ECGs);
- Concomitant medications/therapy.

8.11.3 Immunogenicity Parameters

The following are defined as immunogenicity parameters:

- Development of ADA. If confirmed ADA positive, the following may be determined:
 - Estimation of ADA titers
 - Neutralizing capacity
 - Isotype
 - Epitope map

8.11.4 Exploratory Parameters

The following are defined as exploratory parameters:

- BSSL concentration;
- Inflammatory biomarkers (except BSSL): CRP, ESR for all subjects/patients, and S-calprotectin and hsCRP (only RA patients);
- Cytokine/chemokine panel (including but not limited to IFN γ , IL-1 β , IL-6, IL-10, IL-12, IL-18, MCP-1 and TNF α);
- Flow cytometry panel (only RA patients);
- Whole blood stimulation assays (only RA patients).

9 SAFETY DEFINITIONS AND REPORTING REQUIREMENTS

9.1 Adverse Events

9.1.1 Definitions of Adverse Events

Any untoward medical occurrence in a patient or clinical investigation subject administered a pharmaceutical product and which does not necessarily have a causal relationship with this treatment. An AE can therefore be any unfavorable and unintended sign (including an abnormal laboratory finding), symptom, or disease temporally associated with the use of a medicinal (investigational) product, whether or not related to the medicinal (investigational) product (International Council for Harmonization (ICH) E6; Section 1.2).

A treatment-emergent AE is any AE temporally associated with the use of a study drug, whether or not considered related to the study drug.

Adverse events include:

- Exacerbation of a pre-existing disease.
- Increase in frequency or intensity of a pre-existing episodic disease or medical condition.
- Disease or medical condition detected or diagnosed after study drug administration even though it may have been present prior to the start of the study.
- Continuous persistent disease or symptoms present at baseline that worsen following the start of the study.
- Lack of efficacy in the acute treatment of a life-threatening disease.
- Events considered by the Investigator to be related to study-mandated procedures.
- Abnormal assessments, e.g., ECG, vital signs or physical examination findings, must be reported as AEs if they represent a clinically significant finding that was not present at baseline or worsened during the course of the study.
- Laboratory test abnormalities must be reported as AEs if they represent a clinically significant finding, symptomatic or not, which was not present at baseline or worsened during the course of the study or led to dose reduction, interruption or permanent discontinuation of study drug.

Adverse events do not include:

- Medical or surgical procedure, e.g., surgery, endoscopy, tooth extraction, transfusion. However, the event leading to the procedure is an AE. If this event is serious, the procedure must be described in the SAE narrative.
- Pre-existing disease or medical condition that does not worsen.
- Situations in which an adverse change has not occurred, e.g., hospitalizations for cosmetic elective surgery or for social and/or convenience reasons.
- Overdose of either study drug or concomitant medication without any signs or symptoms. However, overdose must be mentioned in the Study Drug Log.

